6.7 Pre-post salivary cortisol and DHEA testing (Group A and B)

Cortisol is a widely studied biomarker frequently used as a measure of human stress levels (Adam et al., 2017; Ahmed et al., 2023; Smyth et al., 2020). It is a steroid hormone essential for many vital processes, helping to control metabolism, fight infection, regulate blood glucose, maintain blood pressure, and plays an important role in priming the body to respond to stress. Cortisol is produced by the adrenal glands that sit on top of the kidneys and the amount of cortisol released can be influence by a variety of elements including exercise. Levels follow a daily pattern (the diurnal rhythm), rising in the early morning, peaking about 8 a.m. before falling in the evening (Pathology Tests Explained, 2023).

Dehydroepiandrosterone (DHEA) is an adrenal androgen, a human steroid and precursor to several anabolic steroids, which is co-released with cortisol. The cortisol-DHEA ratio hypothesis maintains that DHEA has a protective function in which it counters elevated cortisol to achieve homeostasis, and hence protects the hippocampus and hypothalamic-pituitary-adrenal axis against the effects of chronic exposure to cortisol. It is considered therefore that high levels of DHEA are a good measure of resilience. A comprehensive review of the literature on cortisol and DHEA levels in mental health monitoring found that quantifying the cortisol-DHEA ratio was important for objectively measuring stress variance between mental health service consumers and healthy individuals (Ahmed et al., 2023).

To ensure accurate measurements, samples should be collected at the same time of day for pre- and post-intervention collections. Saliva samples will be collected from all participants by the site study co-ordinator as per the instructions of the test used (see Section 6.7.1). To reduce the possibility of diurnal changes and other confounding variables it is envisaged that the samples will be collected between 11am and 1pm on three assigned collection days, as follows:

- One week prior to the first walk,
- At the conclusion of the first walk,
- At the conclusion of the final walk (12th walk).

Samples will be provided by participants as per the Salimetrics instructions provided by the Salivary Bioscience Research Centre (see Section 6.7.1). The samples will be identified with the participant's unique code to protect their identity before being securely stored for transportation to a freezer at the Rural Health Research Institute, Orange, and University of Wollongong School of Medicine & Health Nutrition Lab where they will be securely stored until transported as a single batch from each site by transportation recommended by the Salivary Bioscience Research Centre to their laboratory in the School of Psychology at the University of New South Wales, Kensington. Samples remain stable for two hours at 2-8C allowing for transportation on ice in a regular esky from the collection site to the secure freezer at either Orange or Wollongong. Samples must then be kept frozen at -20C until testing as thawing and re-freezing degrades the sample.

6.7.1 Saliva collection procedure via passive drool method

Salivary samples for cortisol and DHEA testing should be collected at the same time of day for all samples.

6.7.1.1 Preparation

1. Ensure the tube is labelled with your unique participant code.
2. Remove lipstick or lip balm and avoid brushing or flossing your teeth for at least 30 minutes prior to collection of saliva.
3. It is best not to eat, drink anything but water, or smoke for at least 30 minutes before providing the saliva sample.

6.7.1.2 Collection

Whole saliva samples will be collected with SalivaBio's 2mL cryovials and the Saliva Collection Aid (exclusively from Salimetrics, State College, PA), a collection device specifically designed to improve volume collection and increase participant compliance, and validated to use with salivary analytes, as per the instructions below.

Step 1:
If packaged, open foil pouch and remove the Saliva Collection Aid (SCA). Otherwise, proceed to Step #2.

Step 2:
Place ribbed-end of the SCA securely into a pre-labeled collection vial (see *Caution 3 above*).

Step 3:
Allow saliva to pool in mouth. Then, with head tilted forward, **gently** guide saliva through the SCA into the vial. Fill to the required volume.*

Step 4:
Remove and discard SCA. Attach cap to collection vial and tighten.

*NOTE: Reserve a small amount of air space in the vial to accommodate liquid expansion during freezing.

6.7.1.3 Sample handling

- Immediately after collection, freeze samples at or below -20C. If freezing is not possible, refrigerate immediately at 4C and maintain at this temperature for no longer than necessary (ideally less than 2 hours) before freezing at or below -20C (the temperature of a regular household freezer).
- Samples stored for more than 4 months should be frozen at -80C.

6.8 Before and after walk mood scale (Group A)

Visual single item mood scales have been shown to be both simple and quick to administer and have validity equal to other more complex and time-consuming self-rated or observe-rated scales making them a reliable measure for monitoring mood changes during research projects (Gertler & Tate, 2020; Kontou et al., 2012). A visual single item mood scale typically consists of two dichotomous endpoints with a single straight line about 100mm long. The moods at the endpoints are labeled with a numbered scale, each point represented by an emoji (e.g., 😊 and 😞). Prior to each walk, the research assistant (social work student TBA), will ask each participant to complete their scale before the walk, and then again after (see Appendix 12.8).

6.9 Phone interviews (Group A)

Individual phone interviews will be conducted with the participants of Group A 3 months after the intervention ends. A semi-structured interview guide will be used (see Appendix 12.11); interviews will be audiotaped and transcribed. The brief interview (15-30min) will explore any longer-term benefits for Group A including if they continued to walk in nature. The interviews will be conducted by the project investigators and/or research assistants.

7 DATA ANALYSIS

A frequentist statistical approach will be adopted for quantitative data analysis, using SPSS or R software. Specifically, analysis of variance will provide objective evidence of the efficacy of the NWG intervention.

7.1 Sample size and power calculation

While sample size calculation is crucial for a pilot study, achieving adequate power through formal calculations can be challenging (Billingham et al., 2013). Nonetheless, we have derived the sample size for this study by considering the estimated effect size observed in the literature for various mental health indicators. According to the conceptual framework of the proposed pilot feasibility trial study, the primary outcome measure was the level of distress measured by Patient Health Questionnaire Anxiety and Depression Scale (PHQ-ADS). In a recent randomized controlled trial study in the UK conducted by Picariello et al. (2024), it was found that the mean level of distress among the study participants was 22.76 (SD, 9.46), which decreased by 30% immediately after the cognitive behavioural therapy intervention. We utilized these study findings to inform the parameters for the sample size calculations in our study. We assumed the mean level of distress will be about 22.76 (with SD, 9.46) among the study participants at baseline in both control and interventions group (Picariello et al., 2024). After the program implementation, the mean level of distress will be reduced to 16.08 (SD, 10.41) among the participants in interventions group (assuming about 30% reduction by the intervention; Picariello et al. (2024). To ensure a minimum detectable difference in the mean distress level between the intervention and control groups at follow-up, with a power of 80% and a 5% level of significance, a minimum sample size of 72 participants is required (36 participants in each group). Anticipating 10% loss to follow-up, we plan to include 80 participants in total. Therefore, data will be collected from at least 40 participants in both the control and intervention groups, enabling to assess the program's effectiveness in improving mental health outcomes. Our planned sample size falls within the range of suggested sample sizes for pilot and feasibility studies as per the guidelines, which recommend 30-59 participants (Billingham et al., 2013; Viechtbauer et al., 2015).

The outcomes will be analysed using a Wilcoxon signed ranks test to calculate change between scores because measures contain ordinal data and a test that does not assume a normal distribution is required. A W-statistic is appropriate for a small number of linked observations.

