Participants in Group A will then participate in the NWG intervention. Group A participants will be asked to complete a brief mood scale before and after each walk, and a researcher will complete ethnographic observations during the walk. Follow-up surveys will be completed by those in Groups A and B following the final walking group, and 3 months post-intervention.

Individuals who participated in the NWGs (Group A) will also be invited to a closing reflective focus group at the end of the twelfth walk to discuss their experiences of the groups. Follow-up phone interviews will be conducted with participants from Groups A to find out if they continued walking in nature and any reported longer term impact of the groups. Nature Walking facilitators (Group C) will be invited to participate in a focus group on their experiences delivering in the program.

De-identified aggregated client data to develop a descriptive profile of people using the services will be

provided by each participating site. Group A and B participants will be invited to participate in a member-checking workshop at the conclusion of data analysis. Any changes identified during these workshops will be incorporated into the final findings. Participants will be paid for completing measures as per the schedule listed at Section 10.3.

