5.2 Training workshop (Group C)

NWG facilitators for each site and the research team will attend training and implementation workshops in February 2024 to provide training to facilitators which ensures adequate practitioner knowledge and skills, and practical guidance on nature routine implementation processes and the participant recruitment and data collection tools. Potential facilitators will be identified by site study co-ordinators (PD and TC) and invited to attend the training workshop.

Table 1 - Data collection methods and corresponding aims

		RE-AIM component				
		Reach	Efficacy	Adoption	Implementation	Maintenance
Aims	Data collection tool (planned data analysis approach)					
1. Implementation of NWG	Organisational readiness survey (Descriptive analysis)			x		
	Ethnographic observations during NWG (Thematic analysis)				x	
	Closing reflective focus group (Thematic analysis)				x	
	Facilitator post focus group (Thematic analysis)			x	x	
	De-identified site wide client data (Descriptive analysis)	x				
	NWG attendance records (Attendance ratio calculations)				x	
2. Impact of NWG	Pre/post and 3 month follow-up survey (Wilcoxon signed ranks)^		x			
	Pre-post salivary cortisol and DHEA testing (Change analysis)		x			
	Before and after mood scale (Change analysis)		x			
1 + 2. Impact and implementation	Phone interviews (Thematic analysis)		x		x	
3. Develop implementation and evaluation guidelines	Member-checking workshop (Thematic analysis)					x
	Site comparisons (Data triangulation)				x	x
	Data guide feedback (Guide draft reviewed)					x

^The Patient Health Questionnaire – Anxiety and Depression Scale is the primary outcome measure.

Key

RE-AIM Component	Reach	Identify characteristics, perceptions, and health service utilisation NWG participants, compared to control.
	Efficacy	Identify changes in nature connection, wellbeing, social isolation, quality of life and confidence/self-esteem for participants and control. Understand what worked for different groups and why.
	Adoption	Explore facilitator and management experiences and the implementation barriers and facilitators. Identify similarities and differences in NWG implementation and impacts between sites.
	Implementation	Monitor the implementation process and the experiences of participants.
	Maintenance	Ensure findings and recommendations reflect the lived experience of participants and inform the NWG implementation and evaluation guide.

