6.6 Pre, post and 3-month follow-up Surveys (Group A and B)

An online or pen and paper survey (See Appendix 12.6) will be completed by participants in groups A and B at baseline, 12 weeks post-baseline (post NWG) and at 3 post-intervention. The following scales will be included:

Table 4 - Pre, post and 3-month follow-up survey scales

Primary Outcome Measure	The Patient Health Questionnaire for Anxiety and Depression (PHQ-AD) (16 items)
Secondary Outcome Measures	Personal Wellbeing Index (7 items)
	Pittsburg Sleep Quality Index (2 items)
	DeJong Gierveld Loneliness Scale (6 items)
	Nature Relatedness Scale – short form (6 items)
	The Warwick Edinburgh Mental Well Being Scale (7 items)
	Major life event, positive or negative (2 items)
	Connor-Davidson Resilience Scale (2 items)

In addition, participants in the NWG will be asked to report their mood pre- and post-walking session, as described in Section 6.8.

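### Section 7.1 powers one PHQ-ADS comparison at an undefined follow-up, and the protocol does not say whether the 12-week or the 3-month survey is primary

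*Protocol*

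**What the plan says.** The note under Table 1 (protocol section 5.2) names the measure: "The Patient Health Questionnaire – Anxiety and Depression Scale is the primary outcome measure". Section 7.1 repeats that "the primary outcome measure was the level of distress measured by Patient Health Questionnaire Anxiety and Depression Scale (PHQ-ADS") is primary. Neither statement gives a time.

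Section 6.6 has the survey "completed by participants in groups A and B at baseline, 12 weeks post-baseline (post NWG) and at 3 post-intervention". The unit after the 3 is missing in that sentence, but the section heading supplies months. Table 6 marks weeks 1, 13 and 26. There are therefore two PHQ-ADS measurements after baseline.

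Section 7.1 sets its target as "To ensure a minimum detectable difference in the mean distress level between the intervention and control groups at follow-up, with a power of 80" per cent, and continues with "a 5% level of significance, a minimum sample size of 72 participants is required (36 participants in each group").

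The term follow-up is used in different ways:
- Section 3 covers both surveys with it: "Follow-up surveys will be completed by those in Groups A and B following the final walking group, and 3 months post-intervention".
- The payment list in section 10.3 pays separately for a post-intervention survey and a follow-up survey, so there the bare word means the 3-month survey only.
- Tables 1 and 4 attach 3 months to the word when they mean the later survey. The Table 1 row reads "Pre/post and 3 month follow-up survey (Wilcoxon signed ranks"), with one analysis for all occasions.

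**The concern.** The time of measurement is part of the definition of a primary outcome and of what a sample size is for. Section 7.1 does fix a time, but with a word that the protocol applies to two surveys about three months apart. Two careful readers could report different primary results from the same data, and both could cite the protocol. If the choice were made after the results were seen, or if either survey were allowed to count, the stated 5% level would no longer describe the primary claim. If 3 months were meant, the 80% power would rest on an effect size taken from a different moment.

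**Working it through.** **1. Reproduce the plan's figure.** Inputs, all from section 7.1: control mean 22.76 (SD 9.46), intervention mean 16.08 (SD 10.41), 80% power, 5% level, equal groups, 10% loss. Assumptions: a two-sided test, since sidedness is not stated, and a control mean that stays at its baseline value.

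- Difference: 22.76 − 16.08 = 6.68.
- Average-variance SD: √((9.46² + 10.41²)/2) = √((89.49 + 108.37)/2) = √98.93 = 9.95.
- Standardised difference: 6.68/9.95 = 0.672.
- Normal approximation: n per group = 2(1.960 + 0.842)²/0.672² = 34.8, so 35.
- Two-sample t-test (noncentral t): 35 per group gives power 0.791 and 36 gives 0.802, so 36 per group and 72 in total.
- Loss: 72/0.90 = 80.

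The plan's 36 per group and 80 in total are reproduced. A one-sided 5% test would need only 28 per group by the normal approximation, so the calculation is for **one** two-sided test at **one** time.

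**2. Which time do the inputs support?** Section 7.1 takes its 30% fall from a measurement made directly after the cited therapy, and applies the mean of 16.08 to participants once the programme has been delivered. Neither input describes a state three months later. The effect assumptions therefore support the 12-week survey and say nothing about the 3-month one.

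**3. What if either time could count?** For two tests at two-sided 5% with no true effect, the chance of at least one false positive is 1 − P(|Z₁| < 1.96 and |Z₂| < 1.96). With independent tests this is 1 − 0.95² = 9.75%. The protocol gives no correlation between the two test statistics, so a range is assumed (bivariate normal):

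| Assumed correlation | At least one false positive |
|---|---|
| 0 | 9.75% |
| 0.3 | 9.5% |
| 0.5 | 9.1% |
| 0.7 | 8.4% |
| 0.8 | 7.8% |
| 0.9 | 7.0% |

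**4. What would two co-primary times cost?** With a Bonferroni split (2.5% each), 80% power at each time needs 43 per group (normal) or 44 (t), that is 86 to 88 evaluable participants. With 36 per group, power at each time falls to about 0.71 to 0.73. Naming one time leaves 72 unchanged.

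**5. Does the stated test fit the powered comparison?** Section 7.1 sizes a difference between two groups. The analysis it then names, as does Table 1, is the Wilcoxon signed ranks test, which compares two linked measurements on the same people. It can show change within Group A or within Group B, but it cannot test A against B. The opening of section 7 mentions analysis of variance without saying which groups or times it covers.

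**The case against.** The best defence is that 7.1 can be read correctly in context. It moves from an effect just after treatment, to the mean once the programme is done, to the comparison, and it never mentions 3 months. Where Tables 1 and 4 mean the later survey they say 3 months, so they do not reserve the bare word for it. This stands as far as it goes: 12 weeks is the better reading. It remains an inference, though, because sections 3 and 10.3 use the word in ways that allow another answer.

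A reader might go further and infer that the plan tests PHQ-ADS twice, each time at 5%, and so fails to hold its error rate. The protocol does not support that. The 5% appears once, for one comparison, and nothing says that either time may carry the claim. The figures in step 3 are also a general result for two between-group tests. Under the methods actually named, the number of tests and their correlation are not known.

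A reader might also want to put a number on power lost at 3 months, or on how often the two times would disagree. That requires a guess at how far the effect fades, which the protocol does not give, and disagreement caused by real fading is not an error.

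Two further objections have some weight. Test order and multiplicity are often left to the SAP, so their absence is not raised here; the point is that 7.1 does fix a time, and does so ambiguously. The study also describes itself as a pilot with groups formed by choice or screening result, and naming a time point does nothing for that comparability. But 7.1 still sets 80% power and a 5% level in order to assess effectiveness, so the comparison it powers should be identifiable.

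**Conclusion.** The point holds as an ambiguity in the definition of the primary comparison. PHQ-ADS has two measurements after baseline, 7.1 powers one of them under a word used for both, and only the 12-week survey matches the effect assumptions. The sample size is not wrong: it reproduces as one two-sided 5% t-test with power 0.802 at 36 per group. The error rate of about 7.0% to 9.75% is conditional. It applies only if both times are tested at two-sided 5% and either may count, and it depends on an assumed correlation between 0.9 and 0. Separately, the signed ranks test cannot evaluate the powered comparison, so clarifying the time alone would leave the primary comparison without a usable analysis.

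**What to change.** - In section 7.1, replace the words at follow-up with: at the 12-week post-intervention survey. State that the 5% level is two-sided.
- In Tables 1 and 4, name PHQ-ADS at 12 weeks, Group A versus Group B, as the single primary comparison. List PHQ-ADS at 3 months as a secondary result on maintenance.
- In Table 1 and section 7.1, assign the primary comparison a between-group analysis consistent with the two-group calculation. The signed ranks test can remain for describing change within each group.

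The cost is an edit to these places plus a change of analysis for the primary comparison, so it is slightly more than rewording. No new data or participants are needed: the requirement stays at 72, or 80 with 10% loss. The small downside is that a significant result at 3 months alone could not be presented as the primary finding.

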5.3 Sample

The study will have three groups of participants:

- A. Intervention group - people using the mental health services of the partner organisation at the case study sites (n=40) who will participate in the walking groups,
- B. Non-walking group - people using the mental health service of the partner organisation who choose not to participate in the walking groups, but consent to be involved in the research (n=40), and
- C. NWG facilitators - employees of the partner organisations responsible for service delivery at the case study sites (n=10).

Forty participants will be recruited at each site (ICMHS and LikeMind) (n=80) from the mental health consumers receiving services. Approximately 100 consumers receive services at these agencies at any given time.

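### No stated method gives a baseline-adjusted A-versus-B estimate of PHQ-ADS, although everyone has a baseline score and the groups are self-selected

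*Protocol*

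**What the plan says.** Section 7.1 names the primary outcome: "the primary outcome measure was the level of distress measured by Patient Health Questionnaire Anxiety and Depression Scale (PHQ-ADS"). Its planning values are a common starting level ("We assumed the mean level of distress will be about 22.76 (with SD, 9.46) among the study participants at baseline in both control and interventions" groups) and an improved level after the programme ("the mean level of distress will be reduced to 16.08 (SD, 10.41) among the participants in interventions group"). The target is a "minimum detectable difference in the mean distress level between the intervention and control groups at follow-up". The calculation is run "with a power of 80% and a 5% level of significance", which leads to 36 per group and 80 in total after 10% loss.

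Three places in the protocol speak to analysis:

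- Section 7: "Specifically, analysis of variance will provide objective evidence of the efficacy of the NWG intervention". The type of ANOVA, the form of the outcome and the model terms are not given.
- Section 7.1, last paragraph: the outcomes go to a Wilcoxon signed ranks test on change. The reasons given are ordinal data and the wish not to assume normality.
- Table 1: the survey, which includes the primary outcome, is assigned to the same signed ranks test.

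The data for an adjusted comparison are already planned. Under section 6.6 the survey "will be completed by participants in groups A and B at baseline, 12 weeks post-baseline (post NWG") and again at the 3-month follow-up. Site is known for everyone: "Forty participants will be recruited at each site (ICMHS and LikeMind) (n=80) from the mental health consumers receiving services". Sections 5.3.1, 5.3.2 and 5.4 show that the groups are not randomised. Group A is made up of interested people who pass a health assessment. Group B is made up of people who are not interested, do not pass, or are judged unable by a physician.

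**The concern.** The contrast used for sizing compares A with B but ignores the baseline score. The test assigned to the outcomes uses the baseline score but works within person, so it does not compare A with B. The ANOVA could compare A with B, but the protocol does not say how, or with what use of baseline. None of the three is a baseline-adjusted group comparison.

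Two things are at stake. The first is precision: a person's starting distress is likely to predict their later distress, and using it costs almost nothing. The second is interpretation: the sizing assumes equal starting means, but groups formed by interest and by health screening may well start apart. Part of such a gap would then appear in a raw follow-up difference and could be read as a programme effect.

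**Working it through.** **Inputs.** From section 7.1: means 22.76 and 16.08, SDs 9.46 and 10.41, 36 per group, 5% level. The level is taken as two-sided, which reproduces the stated size. Control is taken to stay at 22.76 (SD 9.46), as the calculation implies. Assumed, because the protocol gives no figure: baseline/follow-up correlation ρ from 0.3 to 0.6, and an illustrative baseline gap of 3 points.

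**Step 1: reproduce the plan's figure.**
- Difference = 22.76 − 16.08 = 6.68.
- Combined SD = √((9.46² + 10.41²)/2) = 9.95.
- A two-sample t-test at 80% power needs 36 per group, 72 in total. Then 72/0.9 = 80. Both stated figures reproduce as an unadjusted comparison of follow-up means.
- SE = √((10.41² + 9.46²)/36) = 2.344. Noncentral t power with 70 df = 80.2%.

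**Step 2: power under the alternatives, 36 per group.**
- Baseline-adjusted: SE = 2.344 × √(1 − ρ²), 69 df. A further df for site changes power by less than 0.1 point.
- Change score: variance in A = 9.46² + 10.41² − 2ρ(9.46)(10.41); variance in B = 2(9.46²)(1 − ρ); SE = √((var A + var B)/36).

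| ρ (assumed) | Raw follow-up | Change score | Baseline-adjusted |
|---|---|---|---|
| 0.3 | 80.2% | 68.2% | 83.8% |
| 0.4 | 80.2% | 74.8% | 86.6% |
| 0.5 | 80.2% | 82.0% | 90.0% |
| 0.6 | 80.2% | 89.5% | 94.0% |

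At ρ = 0.5 the SE falls from 2.34 to 2.03. With two time points, the group-by-time test of a repeated-measures ANOVA is the change-score comparison, so that column also covers that reading of section 7.

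**Step 3: what a baseline gap does.** Take a 3-point gap, ρ = 0.5, equal spread and no true effect. The answer depends on how the gap behaves over time.

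| Spurious difference (points) | Raw follow-up | Change score | Baseline-adjusted |
|---|---|---|---|
| Gap regresses to a common mean | 0.5 × 3 = 1.5 | 1.5 − 3 = −1.5 | 1.5 − 0.5 × 3 = 0 |
| Groups have stable, different levels | 3 | 3 − 3 = 0 | 3 − 0.5 × 3 = 1.5 |

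In the first row, 1.5/6.68 = 22% of the target effect. The shift is 1.5/2.344 = 0.64 standard errors, which takes a nominal two-sided 5% error to about 10%. In the second row, baseline adjustment halves the spurious difference but does not remove it.

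**The case against.** Covariates are often left to a SAP, and section 7 is one sentence naming a family of methods. A reader might infer that the protocol prescribes a plain ANOVA on raw follow-up scores. It does not: the follow-up wording is in the sample-size paragraph, and with three survey waves a repeated-measures ANOVA fits section 7 equally well. That part of the objection stands. But the protocol itself fixes the sizing contrast and the signed ranks test, and neither gives an adjusted A-versus-B estimate. The repeated-measures reading reduces, for two time points, to the less efficient change score.

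A reader might also infer that the study is underpowered. It is not, on its own inputs. Sizing without a correlation is ordinary practice, and the gain from adjustment is under 4 points at ρ = 0.3.

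The strongest objection concerns bias. In non-randomised groups it cannot be claimed that change scores always over-correct, or that baseline adjustment removes the bias. If the groups have stable, different levels, the change score is the unbiased one. This stands, and it is why a change-score sensitivity analysis is needed. It does not affect the efficiency comparison.

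Finally, site need not confound A with B. Two walking groups of 10 at each site give 20 in Group A, which leaves 20 of the 40 per site for Group B. The protocol shows no site effect, so site is a sensible design covariate and not a demonstrated source of error.

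**Conclusion.** The point holds in a limited form. The protocol collects baseline PHQ-ADS from everyone in two self-selected groups, yet it states no method that gives a baseline-adjusted comparison between them. The planned 80% power is met without adjustment. What is forgone is about 4 to 14 percentage points of power relative to a baseline-adjusted model, for correlations of 0.3 to 0.6, which are assumed. Over that range the adjusted model also beats the change score, by about 4 to 16 points. The bias figure of 1.5 points is an illustration that rests on an assumed 3-point gap, a correlation of 0.5 and regression to a common mean. Under stable group differences the bias has a different size, and adjustment removes only part of it. The documents support neither a claim that the design lacks power nor a claim that adjustment would make the groups comparable.

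**What to change.** - In section 7, state the primary between-group analysis as a linear model of 12-week PHQ-ADS on group, with baseline PHQ-ADS and site as covariates. Use the same form for the secondary scales, each with its own baseline, and for the 3-month survey.
- For the primary between-group result, put this model in place of the Wilcoxon entry in Table 1 and the Wilcoxon sentence in section 7.1. Keep the signed ranks test only as a descriptive within-group summary.
- Answer the stated concern about ordinal data and normality with robust or bootstrap standard errors, or with a rank-based ANCOVA as a sensitivity analysis.
- Add a change-score sensitivity analysis because the groups are not randomised, and state that unmeasured confounding remains.
- Keep 36 per group, described as a conservative unadjusted figure.

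The cost is two degrees of freedom, a little more analysis work and a few sentences of text. No new data or participants are needed.
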